**Aim 2. Evaluate the effect of sildenafil on clinically relevant outcomes in subjects with CF**

- a. Evaluate the effect of sildenafil on lung function in subjects with CF
- b. Evaluate the effect of sildenafil on weight in subjects with CF
- c. Evaluate the effect of sildenafil on pulmonary exacerbations in subjects with CF
- d. Evaluate the effect of sildenafil on quality of life in subjects with CF

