**Aim 3. Further evaluate the safety and tolerability of sildenafil in subjects with CF**

- a. Evaluate the effect of sildenafil on treatment emergent adverse events
- b. Evaluate the effect of sildenafil on change in clinical laboratory measures, vital signs and physical exam findings

Primary Endpoints

Na+ conductance by nasal potential difference (within subject change in maximum basal PD)

Secondary Endpoints

Other measures of Na transport (mean basal PD, end-ringers profusion PD, change in PD with amiloride)  
 Cl conductance by NPD (total Cl conductance, change in PD with chloride free solution, change in PD with isoproteronol, total change in NPD (delta NPD))  
 Sweat Na+ by pilocarpine iontophoresis  
 Sweat Cl concentration by pilocarpine iontophoresis  
 Pulmonary function by spirometry  
 Lung clearance index  
 Exhaled nitric oxide (eNO)  
 Sputum nitric oxide metabolites  
 Safety and tolerability (including laboratory studies, CFQ-R)

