Study visit (visit 4; Day 29 $\pm$ 3): Subjects will return to the study site for visit 4. CFR-Q will be administered. A complete physical exam will be performed to include vital signs and NER, and adverse events will be assessed. eNO and spirometry will be performed. Spontaneously expectorated sputum will be collected. Safety labs and a sildenafil trough level will be drawn. Each subject will undergo pilocarpine iontophoresis with sweat collection, nasal potential difference testing, and lung clearance index testing. Clinical laboratory tests will be performed including CBC with differential, chemistry profile, INR (total of 10cc of blood), and a urine pregnancy test (for females of child-bearing potential). Medication bottles will be collected.

Study visit (visit 5; Day 43 $\pm$ 3): Two weeks following study completion, the research coordinator will call subjects to determine if any adverse events have occurred or if there have been any changes in concomitant medications.

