#### Early Withdrawal

In case of early withdrawal, an Early Withdrawal Visit will be scheduled within 7 days following the last dose of study medication. Physical exam will be performed by the primary investigator including weight, temperature, blood pressure, respirations and pulse oximetry. Spirometry will be performed. Subject will undergo pilocarpine iontophoresis with sweat collection, nasal potential difference testing, and lung clearance index testing. Any abnormal findings will be documented. Clinical laboratory tests will be performed including CBC with differential, chemistry profile, and urine pregnancy test (for females of child-bearing potential.) Medication bottles will be collected.

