### Outcome measurements and Procedures

Nasal exam rating score will be performed at each visit using the validated system established by the CF TDN Center for CFTR Detection.

Spirometry will be performed at the visits according to ATS standards.

Spontaneously expectorated sputum will be collected for measurement of NO metabolites at the initiation and final visits.

Exhaled nitric oxide will be collected prior to spirometry according to ATS standards. Subjects will be instructed not to eat or drink for 1 hour prior to eNO measurements.

Pilocarpine iontophoresis will be performed and sweat collected according to CFF standards. Sweat volume will be recorded and sweat rate collected. Sweat will be collected using the Macroduct® collection system. Samples will be shipped to the TDN Core laboratory in Aurora, CO for sodium and chloride concentration measurement.

Nasal potential difference will be performed according to CF TDN standard operating procedure (SOP 528.01) Interpretation and analysis of results will be performed by a blinded investigator at the University of Alabama.

Lung clearance index (LCI) is a measure of ventilation inhomogeneity that is obtained by multiple breath washout. It has been shown to be more sensitive than FEV1 in detecting mild lung function abnormalities, and has been endorsed by the European CF Society Clinical Trial Network Standardization Committee. LCI measurement will be performed on an Eco Medics device using 100% O2 as described by the ECSF-TDN.

The CFQ-R is designed to measure CF-specific patient-reported health-related quality of life. The 48 questions encompass five domains including physical symptoms, role functioning (e.g. school/work), psychological and emotional functioning, energy/fatigue, and social functioning. The four domains specific to CF that are measured are: eating disturbances, body image, embarrassment caused by symptoms, and treatment burden. This questionnaire has been validated in CF patients. The questionnaire will be administered at the initial and end of treatment visits for each treatment period prior to any procedures.

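### The Early Withdrawal Visit omits CFQ-R, so the quality-of-life comparison (Aim 2d) would rest on completers only

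*Combined protocol and SAP*

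**What the plan says.** The Early Withdrawal section states that "an Early Withdrawal Visit will be scheduled within 7 days following the last dose of study medication". It then itemises the visit: physical exam with weight and vital signs, spirometry, and bottle return, plus "Subject will undergo pilocarpine iontophoresis with sweat collection, nasal potential difference testing, and lung clearance index testing" and "Clinical laboratory tests will be performed including CBC with differential, chemistry profile, and urine pregnancy test". CFQ-R, eNO, sputum and the nasal exam rating are not named.

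Quality of life is Aim 2d: "Evaluate the effect of sildenafil on quality of life in subjects with CF". The secondary endpoints also place the questionnaire inside another item: "Safety and tolerability (including laboratory studies, CFQ-R".

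The narratives for Visit 2 (Day 1) and Visit 4 (Day 29) each say "CFR-Q will be administered", which I read as CFQ-R. The Visit 3 narrative does not. The flowchart marks CFQ-R at Visits 2 and 4 and has no early-withdrawal column.

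Outcome measurements and Procedures is worded more broadly: "The questionnaire will be administered at the initial and end of treatment visits for each treatment period prior to any procedures". For sputum it says: "Spontaneously expectorated sputum will be collected for measurement of NO metabolites at the initiation and final visits". It also calls for the nasal exam rating at every visit.

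Subjects leave the study for not tolerating dose escalation, for a systolic fall of at least 20 mmHg after dosing, for an exacerbation needing hospitalisation, or for an adverse event that the investigator judges to preclude continuing. The study population paragraph says that those who withdraw early are replaced until 18 is reached.

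**The concern.** Visit 4 is the only scheduled post-baseline CFQ-R. A subject who leaves before it has a baseline score and nothing to compare it with, and the replacement subject fills the place in the target of 18. The CFQ-R comparison then describes people who stayed on treatment to Day 29.

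Several of the stated reasons for leaving concern how the subject fared on treatment, so those missing may well differ from those who remain. A value that was never collected can only be imputed under assumptions that the trial cannot test.

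The plan already considers values after withdrawal worth having, since it repeats NPD, sweat, LCI and spirometry there. It gives no reason for leaving out a questionnaire at the same visit.

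**Working it through.** **Schedule, from the visit narratives and the Early Withdrawal list**

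| Measure | Visit 2 | Visit 3 | Visit 4 | Early Withdrawal list |
|---|---|---|---|---|
| NPD, sweat, LCI | yes | yes | yes | yes |
| Spirometry | yes | no | yes | yes |
| CFQ-R | yes | no | yes | no |
| eNO, sputum | yes | no | yes | no |

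A completer has two CFQ-R scores. A subject withdrawn before Visit 4 has one, at baseline. For CFQ-R the flowchart agrees with the narratives. It has no row for eNO, sputum or the nasal exam rating.

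**The plan's own figures.** The documents give no CFQ-R standard deviation, target difference, power or expected withdrawal rate, so there is no stated CFQ-R figure to reproduce. The stated powers are for other endpoints: 100% for maximal basal PD (10.4 mV, SD 2.59) and 95% for sweat chloride (5 mEq, SD 2.6), with 12 and 6 subjects. A two-sided t-test on 16 degrees of freedom returns more than 99.99% and 95.0%. Both reproduce, and this point does not touch them.

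**How often it could arise.** With withdrawal rate p, the chance of at least one withdrawal among 18 subjects is 1 - (1 - p)^18.
- p = 3%: 1 - 0.97^18 = 42%. The 3% is the discontinuation figure for 20 mg t.i.d. in Known Potential Toxicity of Study Drug; carrying it over to this trial is an assumption.
- p = 10% (assumed): 85%.
- p = 20% (assumed): 98%.

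**Size of the gap in the sildenafil arm.** Assume that replacement is within arm, so that 12 sildenafil subjects complete, and that completers change by 0 on average. If w subjects withdraw with mean change m, the all-treated mean is w × m / (12 + w), against a completer mean of 0.
- w = 2, m = -10: 2/14 × -10 = -1.4 points.
- w = 3, m = -15: 3/15 × -15 = -3.0 points.
- 3% of those treated withdraw, m = -10: 0.03 × -10 = -0.3 points.

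The values of w and m are assumptions.

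**Between arms.** The same formula with 6 placebo completers and 1 placebo withdrawal at -10 gives 1/7 × -10 = -1.4, which equals the first sildenafil case. Two withdrawals on sildenafil and one on placebo, all at -10, would therefore cancel in the treatment difference. The direction of any error depends on who withdraws, and the documents do not settle that.

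**The case against.** **The tolerability data survive.** Aim 3 rests on adverse events, laboratory measures, vital signs and physical findings. The Early Withdrawal Visit collects the last three, and the Adverse Events section requires every event to be followed to resolution or stabilisation. This stands. A reader might infer that the trial would wrongly report sildenafil as well tolerated. The documents do not support that, because an intolerance withdrawal is itself visible in the record. The gap is confined to the patient-reported component and to Aim 2d.

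**Differential dropout is not shown.** A reader might also infer more withdrawals on sildenafil. The only discontinuation figures given are 3% on drug and 3% on placebo at 20 mg t.i.d. Some adverse events are said to be more frequent above that dose, and this trial goes to 40 mg, so an imbalance is plausible. It is not established.

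**The broader wording may already cover it.** The sentence on CFQ-R timing could be read to include an Early Withdrawal Visit, as could the sputum sentence. But the itemised list and the flowchart point the other way, and sites are likely to follow those. The CFQ-R sentence also refers to each treatment period, although the dosing section describes only one 28-day course per subject. This is a conflict to reconcile. The nasal exam rating is different: it is required at every visit, so its absence from the list is a matter of wording.

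**Values at this visit may be taken off drug.** The visit can fall 7 days after the last dose, and the stated half-life is about 4 hours. This largely removes the case for eNO and sputum. It also weakens the case for CFQ-R in a subject stopped on Day 1 after a single dose, who completed the questionnaire that day. It carries less weight for someone withdrawn after days or weeks of treatment.

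**The main cause lies elsewhere.** Replacement, and the absence of a stated analysis set, would produce a completers-only comparison in any case. The repeated-measures analysis is specified for NPD and sweat, and no CFQ-R comparison is described. This is correct, and it means that collecting the score must go together with saying how it will be used.

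**Conclusion.** The point holds within limits. Under the itemised list, subjects withdrawn before Day 29 contribute no post-baseline CFQ-R, and Aim 2d would describe completers only. On the assumptions shown, the sildenafil mean would shift by between about -0.3 and -3.0 points. The documents give no CFQ-R variability or important difference, so I cannot say whether a shift of that size would matter. If nobody withdraws, there is no loss.

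A reader might infer that no analysis could help. That goes too far: sensitivity analyses for missing outcomes exist, but here they would rest wholly on assumptions about the missing scores. Nor does the gap reach the primary endpoint, since NPD is measured at early withdrawal. CFQ-R is an unpowered secondary measure in a trial that the protocol itself calls a pilot. The change is worth making because it is cheap and a missed score cannot be recovered later.

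**What to change.** - Add CFQ-R, before any procedure, to the Early Withdrawal Visit, and record the time since the last dose.
- Add an Early Withdrawal column to the flowchart.
- Reconcile both with Outcome measurements and Procedures: whether the end-of-treatment wording for CFQ-R and the final-visit wording for sputum include early withdrawal, and that the nasal exam rating applies at this visit.
- Specify a CFQ-R comparison in Data Analysis that includes all treated subjects, including those later replaced, and uses the early-withdrawal scores. Report withdrawals and reasons by arm beside it.
- eNO and sputum at this visit are optional.

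The cost is a short amendment, one CRF page and a questionnaire already in use, at a visit that already takes place. The downsides are slightly more burden on withdrawing subjects and some scores taken off drug, which the recorded time since last dose makes visible.

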#### Concomitant medications

All subjects should continue the same medications throughout the study period, as medically feasible, with no introduction of new chronic therapies during or <4 weeks prior to enrollment. If a change in concomitant medications is required, the reason(s) for the change(s) will be recorded on the subject's CRF. Subjects who

require hospitalization for the treatment of a pulmonary exacerbation during the course of the trial will be withdrawn from the study.

### Outcome measurements and Procedures

Nasal exam rating score will be performed at each visit using the validated system established by the CF TDN Center for CFTR Detection.

Spirometry will be performed at the visits according to ATS standards.

Spontaneously expectorated sputum will be collected for measurement of NO metabolites at the initiation and final visits.

Exhaled nitric oxide will be collected prior to spirometry according to ATS standards. Subjects will be instructed not to eat or drink for 1 hour prior to eNO measurements.

Pilocarpine iontophoresis will be performed and sweat collected according to CFF standards. Sweat volume will be recorded and sweat rate collected. Sweat will be collected using the Macroduct® collection system. Samples will be shipped to the TDN Core laboratory in Aurora, CO for sodium and chloride concentration measurement.

Nasal potential difference will be performed according to CF TDN standard operating procedure (SOP 528.01) Interpretation and analysis of results will be performed by a blinded investigator at the University of Alabama.

Lung clearance index (LCI) is a measure of ventilation inhomogeneity that is obtained by multiple breath washout. It has been shown to be more sensitive than FEV1 in detecting mild lung function abnormalities, and has been endorsed by the European CF Society Clinical Trial Network Standardization Committee. LCI measurement will be performed on an Eco Medics device using 100% O2 as described by the ECSF-TDN.

The CFQ-R is designed to measure CF-specific patient-reported health-related quality of life. The 48 questions encompass five domains including physical symptoms, role functioning (e.g. school/work), psychological and emotional functioning, energy/fatigue, and social functioning. The four domains specific to CF that are measured are: eating disturbances, body image, embarrassment caused by symptoms, and treatment burden. This questionnaire has been validated in CF patients. The questionnaire will be administered at the initial and end of treatment visits for each treatment period prior to any procedures.

There is no drug interaction between ivacaftor and sildenafil. However, because the lumacaftor portion of Orkambi is a strong inducer of CYP3A, use of Orkambi with sildenafil may decrease sildenafil levels. Based on our previous work, average trough values at steady state for subjects with CF receiving 40 mg of sildenafil t.i.d. were approximately 39 ng/mL. Sildenafil trough levels will be performed at visits 2, 3, and 4 to confirm non-interference of metabolism with co-administration with Orkambi.

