Initiation visit period 1 (visit 2; Day 1): Subjects meeting entry criteria will be evaluated in the outpatient research unit. CFR-Q will be administered. A limited physical exam will be performed to include vital signs and NER. A urine pregnancy test will be done for females of child-bearing potential. eNO and spirometry will be performed. Spontaneously expectorated sputum will be collected. Safety labs and a sildenafil trough level will be drawn. Each subject will undergo pilocarpine iontophoresis with sweat collection, nasal potential difference testing, and lung clearance index testing. Patient will then receive study medication (placebo or sildenafil.) Subsequent to medication dosing, vital signs will be assessed at 1 hour and 2 hours post-dose. A drop in systolic blood pressure of  $\geq 20$ mmHg will be considered intolerance, and the subject will be discontinued from the study.

Subjects tolerating the medication will be discharged with a 7-day supply of placebo or sildenafil 20 mg p.o. t.i.d. Subjects will be instructed to call the study staff (during business hours) or the pulmonary attending on call (after business hours) for any significant adverse events that occur (e.g. severe headache, dizziness, or persistent visual changes.)

Study visit (visit 3; Day 8 $\pm$ 3): After 7 days of therapy, the subject will return to the study site. Vitals signs and adverse events will be assessed. Safety labs and a sildenafil trough level will be drawn. Each subject will undergo pilocarpine iontophoresis with sweat collection, nasal potential difference testing, and lung clearance index testing. Medication bottles will be collected. Subject will then receive study medication (placebo or sildenafil 40 mg). Subsequent to medication dosing, vital signs will be assessed 1 hour and 2 hours post-dose. A drop in systolic blood pressure of  $\geq 20$ mmHg will be considered intolerance. Subjects with intolerance of dose escalation will be discontinued from the study. Subjects tolerating medication will be given 21 days of placebo or sildenafil 40 mg p.o. t.i.d.

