Data from pharmacokinetic analysis will be analyzed using ANOVA in SAS v.9.2. P-values  $\leq 0.05$  will be regarded as significant. Data will be screened for nonnormality, and appropriate transformations as needed (such as log) will be applied; careful residual analysis will be performed to detect outliers and other anomalies. Non-parametric procedures (Proc NPAR1WAY in SAS v9.2) will be applied in cases where transformations do not normalize the data. Carryover effects in the crossover design will be fit initially but discarded if they are not (as expected) significant. Correlations between NPD, sweat chloride and clinical parameters will also be conducted. All statistical analysis will be performed in conjunction with [name] and CCTSI statisticians.

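### Sildenafil troughs are meant to confirm that Orkambi does not interfere, but the only stated pharmacokinetic analysis tests for a difference and cannot establish its absence

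*Combined protocol and SAP*

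**What the plan says.** The purpose is given under Outcome measurements and Procedures. Because lumacaftor induces CYP3A, "use of Orkambi with sildenafil may decrease sildenafil levels". The text gives a reference from the investigators' earlier work: "average trough values at steady state for subjects with CF receiving 40 mg of sildenafil t.i.d. were approximately 39 ng/mL". It then states the aim: "Sildenafil trough levels will be performed at visits 2, 3, and 4 to confirm non-interference of metabolism with co-administration with Orkambi".

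The analysis is given under Data Analysis: "Data from pharmacokinetic analysis will be analyzed using ANOVA in SAS v.9.2", with P-values of 0.05 or less regarded as significant. Two supporting sentences follow: "Data will be screened for nonnormality, and appropriate transformations as needed (such as log) will be applied" and "Non-parametric procedures (Proc NPAR1WAY in SAS v9.2) will be applied in cases where transformations do not normalize the data". Data Analysis does not mention Orkambi. The Sample size section does not cover the trough comparison, and trough is not among the listed endpoints.

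The visit descriptions fix what each sample can show. At visit 2 the trough is drawn first, and only afterwards: "Patient will then receive study medication (placebo or sildenafil". After that visit: "Subjects tolerating the medication will be discharged with a 7-day supply of placebo or sildenafil 20 mg p.o. t.i.d". The visit 3 trough therefore follows a week at 20 mg t.i.d., and the visit 4 trough follows the three weeks at 40 mg t.i.d.

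**The concern.** Confirming non-interference means concluding that an effect is absent, or too small to matter. That needs a stated size of effect to be ruled out, or at least an interval from which a reader can see what has been ruled out. The plan states neither. A test at P≤0.05 can support the statement that Orkambi changes trough. It cannot support the opposite statement, because a non-significant result arises both when there is no effect and when the data are too few or too variable to show one.

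The reference of 39 ng/mL does not fill the gap: it says what was seen before, not how far below it a trough may fall and still count as unaffected.

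The informative data are also few. Placebo subjects contribute nothing. The sildenafil arm has about 12 subjects, Orkambi is optional background therapy, and no stratification by it is stated, so the split is unknown. At stake is the exposure statement in the report: a sentence saying that Orkambi does not affect sildenafil levels could rest on nothing more than P>0.05.

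**Working it through.** **1. The plan's own figures.** Two-sided t-test at 5%, 12 v 6, 16 df, critical t 2.120, SE = SD × √(1/12 + 1/6) = SD × 0.5.
- 10.4 mV, SD 2.59: SE 1.295, noncentrality 10.4/1.295 = 8.03, power >99.9% (stated: 100%).
- 5 mEq, SD 2.6: SE 1.30, noncentrality 5/1.30 = 3.85, power 95.0% (stated: 95%).

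Both reproduce. No corresponding figure exists for trough.

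**2. What each trough can show.**
- Visit 2: drawn before the first dose, so only a pre-dose baseline.
- Visit 3: after 20 mg t.i.d. It allows an Orkambi yes/no comparison within that dose, but not a comparison with the 40 mg reference.
- Visit 4: after 40 mg t.i.d., and the only visit that matches the reference.

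**3. How often the stated test would miss a halving at visit 4.** From the documents: 12 sildenafil subjects and the 0.05 level. Assumed, because the documents give no figure: a two-fold drop as the effect of interest, between-subject CVs of 30 to 80%, lognormal troughs, and splits of 6/6 and 9/3 (9 in one group, 3 in the other).

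Log-scale SD s = √ln(1 + CV²); SE = s × √(1/n₁ + 1/n₂); noncentrality = ln 2 / SE; 10 df; critical t 2.228. Miss probability = 1 − two-sided power from the noncentral t.

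| CV | s | SE 6/6 | ln 2/SE | P>0.05 | SE 9/3 | ln 2/SE | P>0.05 |
|---|---|---|---|---|---|---|---|
| 30% | 0.294 | 0.170 | 4.09 | 4% | 0.196 | 3.54 | 11% |
| 40% | 0.385 | 0.222 | 3.12 | 20% | 0.257 | 2.70 | 32% |
| 60% | 0.555 | 0.320 | 2.17 | 50% | 0.370 | 1.87 | 60% |
| 80% | 0.703 | 0.406 | 1.71 | 66% | 0.469 | 1.48 | 73% |

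A smaller drop is missed more often: for a true 30% reduction with 6/6, P>0.05 in 52% of trials at CV 30% and 78% at CV 50%.

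**4. What an interval would show if there is no true effect.** The probability that the lower 90% limit for the ratio exceeds 0.5 is P(T > 1.812), with T noncentral t on 10 df and the same noncentrality. The half-width, as a fold change either side of the estimate, is exp(1.812 × SE).

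| CV | Excludes a halving, 6/6 | 9/3 | Half-width, 6/6 | 9/3 |
|---|---|---|---|---|
| 30% | 98% | 95% | 1.36-fold | 1.43-fold |
| 40% | 89% | 81% | 1.50 | 1.59 |
| 60% | 64% | 54% | 1.79 | 1.95 |
| 80% | 48% | 39% | 2.09 | 2.34 |

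The same sample can be informative or not. The interval shows which; the P-value does not.

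**5. Reach into the primary endpoint.** If the drug effect were halved in all 12 sildenafil subjects: 10.4/2 = 5.2 mV, noncentrality 5.2/1.295 = 4.02, power 96%.

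**The case against.** The strongest reply is that *confirm* is loose wording for exposure monitoring. The sentence sits under procedures, no decision depends on the result, and no aim or endpoint is pharmacokinetic. The ANOVA sentence names neither trough nor Orkambi and shares a paragraph with crossover text that does not fit this parallel design, so it may be inherited. Part of this stands: the matter is supportive, and the remedy is close to a wording change. The link to the ANOVA survives, however. Troughs are the only pharmacokinetic data the protocol schedules, so either that sentence covers them or no analysis is stated at all. In both cases nothing supports the word *confirm*.

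A second reply is that the miss rates depend on assumptions, including the two-fold threshold. That is right: they illustrate and do not measure this trial. The logical gap does not depend on them.

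Three stronger readings are tempting, and the documents do not support them:
- *The plan treats P>0.05 as proof of no interaction.* It does not say so; it simply gives no other rule.
- *The trial cannot exclude a material drop.* That turns on a CV and an Orkambi split that are not given. At CV 30% with a 6/6 split, a halving would be excluded 98% of the time if there were no effect.
- *Users' troughs can be formally tested against 39 ng/mL.* The text says only that this is an average. If it is arithmetic and troughs are lognormal, the matching geometric mean is 39/√(1 + CV²), about 33 at CV 60%, so unaffected users could look reduced.

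**Conclusion.** The point holds, at low severity. The stated aim is a conclusion of no effect, the stated analysis can only detect an effect, and no margin, interval or criterion connects the two. This follows from the text alone.

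Its size is conditional. If trough were truly halved, the visit 4 test would be non-significant in 4/20/50/66% of trials with a 6/6 split, or 11/32/60/73% with 9/3, at CVs of 30/40/60/80%. The two-fold drop, the CVs and the splits are all assumptions.

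The consequence stops at the exposure conclusion. A reader might infer that the primary comparison is weakened, but trough is not a listed endpoint, and on the Sample size figures even a halved effect throughout the sildenafil arm leaves 96% power.

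**What to change.** In Outcome measurements and Procedures, change the purpose of the troughs to: *to estimate the effect of Orkambi on sildenafil trough*. In Data Analysis, add:
- In the sildenafil arm, report the Orkambi/no-Orkambi geometric mean trough ratio with a 90% confidence interval at visit 4, and within dose at visit 3, with individual values shown.
- Describe visit 4 values against 39 ng/mL without a test.
- Use visit 2 only as a pre-dose baseline.
- State that a non-significant ANOVA will not be read as no interaction.

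Adding an equivalence margin instead is not realistic at this size. With an assumed range of 0.80 to 1.25 and a 6/6 split, the chance of meeting it with no true effect is 1.7% at CV 30% and about zero at CV 50% or more.

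The cost is one changed sentence and a few lines of analysis text, with no extra samples or subjects. The downside is that the protocol gives up the claim of confirmed non-interference.
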